4.3. Treatment Compliance

Summaries of subjects' compliance information will be reported through tables for wear time and comfortable wear time.

4.4. Protocol Deviations

All reported protocol deviations will be listed.

4.5. Prior and Concomitant Medications

Listings of subjects' prior and concurrent medications will be reported.

4.6. Discontinuation

All reasons for discontinuation will be listed including lens type being used at time of discontinuation.

5. EFFICACY

5.1. Analysis Specifications

5.1.1. Level of Significance

All planned analysis for this study will be conducted with a two-sided type I error rate of 5% for primary and secondary hypotheses. Adjustment for multiple comparisons across time will be performed using Bonferroni's method. Both adjusted and unadjusted results will be reported.

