5.2.2. Analysis Methods

Efficacy Analysis:

Visual Acuity

Contact lens monocular distance best-corrected visual acuity (BCVA) on LogMAR scale will be analyzed using a linear mixed model to test for the differences between the Test and Control group at each follow-up visit. Lens group, time (1-, 2-, 4-, 8- and 12-weeks) and the interaction between lens and time will be included as fixed effects in the model; and investigator site, subject and eye nested within subject as random effects when appropriate. The covariance between residuals from the same eye and subject at different time points will be selected based on the finite-sample Corrected Akaike's Information Criterion. Covariance structures considered include Compound Symmetry (CS), Heterogeneous Compound Symmetry (CSH), Spatial Power (SP(POW)), *Ante*-dependence (ANTE(1)) and unstructured (UN). For ANTE (1) and SP (POW) structures, site, subject and eye nested within subject will be included as random effects. For the remaining structures only site and subjects will be included as random effects. The covariance structure that returns the lowest Akaike Information Criteria Corrected (AICC) will be selected as the structure that best fit the data. Heterogeneous residuals covariance structures (R-side) across lens groups will be considered when appropriate. The log-likelihood ratio test will be used to test for the homogeneity between the residual covariance structures. The Kenward and Roger method will be used for the denominator degree of freedom.

Comparisons between the Test and the Control groups will be conducted at each time point using a t-test on least-square means from the repeated measure analysis. Adjustment for multiple comparisons across time will be performed using Bonferroni's method with alpha equal to 0.01(0.05/5). The corresponding simultaneous confidence intervals of least-square means differences will be calculated with 99% confidence. Unadjusted multiple comparisons will be calculated with 95% confidence for each comparison.

Average Wear Time (AWT)

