AWT (in hours) will be analyzed using a linear mixed model to test for difference between the Test and the Control groups. Lens Group, Time (2-, 4-, 8- and 12-week), and the interaction between lens and time will be included as fixed effects in the model; and site as random effect. The covariance between residuals from the same subject at different time points will be selected based on the finite-sample corrected Akaike's Information Criterion. Covariance structures considered include homogenous compound symmetry (CS), heterogeneous Compound symmetry (CSH), Spatial Power (SP (POW)), Ante-dependence (ANTE (1)) and unstructured (UN). For ANTE (1) and SP (POW) structures, site and subject will be included as random effects. For the remaining structures only site will be included as random effect. The covariance structure that returns the lowest AICC will be selected as the structure that best fit the data. Heterogeneous residuals covariance structures (R-side) across lens groups will be considered when appropriate. The log-likelihood ratio test will be used to test for the homogeneity between the residual covariance structures. The Kenward and Roger method will be used for the denominator degree of freedom.

Comparison between the Test and the Control groups will be conducted at each time point using a t-test on least square means from the repeated measure analysis. Adjustment for multiple comparisons across time (2-, 4-, 8- and 12-weeks) will be performed using Bonferroni's method with alpha equal to 0.0125(0.05/4). The corresponding simultaneous confidence intervals of least-square means differences will be calculated with 98.75% confidence. Unadjusted multiple comparisons will be calculated with 95% confidence for each comparison.

Eyestrain caused by glare score

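### Bonferroni across visits is valid but conservative: a joint-t adjustment of the same-visit contrasts would hold 5% familywise error with intervals no wider, by an amount that depends on an unstated correlation

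*SAP*

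**What the plan says.** SAP 5.1.1 sets a "two-sided type I error rate of 5% for primary and secondary hypotheses", then states "Adjustment for multiple comparisons across time will be performed using" Bonferroni's method, and "Both adjusted and unadjusted results will be reported".

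SAP 5.2.2 carries this out endpoint by endpoint, using t-tests on least-square means at each visit:

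- Visual acuity: five visits, 0.05/5 = 0.01 each. "The corresponding simultaneous confidence intervals of least-square means differences will be calculated with 99% confidence".
- Average wear time and eyestrain: four visits, 0.05/4 = 0.0125 each. For both, "The corresponding simultaneous confidence intervals of least-square means differences will be calculated with 98.75% confidence".

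For all three endpoints the same section estimates the covariance between time points within a subject, choosing among five structures by AICC. Unadjusted 95% intervals are reported beside the adjusted ones. SAP 1.4 and protocol 3.1 call the hypotheses exploratory.

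**The concern.** Bonferroni makes no use of the dependence between comparisons. Here the four or five differences for an endpoint are measured on the same people and come from one fitted model. A subject who scores high at week 4 will tend to score high at week 8, so the differences should be positively correlated. The familywise error then falls below the stated 5%, and the simultaneous intervals are wider than that level requires.

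The model that supplies the t-tests also supplies the joint covariance of the differences, so a sharper adjustment at the same familywise level needs no new data and no new model. Eyestrain has most to gain. It is a co-primary endpoint with a superiority hypothesis, SAP 1.5 gives no power figure for it, and the sample size was not derived from a calculation.

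**Working it through.** **Inputs.** Alpha 0.05 two-sided per endpoint (SAP 5.1.1). Four comparisons for eyestrain and wear time, five for acuity (SAP 5.2.2). Fifty completers per arm (SAP 1.5). Degrees of freedom 2 x 50 - 2 = 98, an assumption, since the Kenward-Roger value is not known in advance. Between-visit correlation: not stated for any of the three endpoints, so 0.10 to 0.90 is assumed, equal between all pairs of visits.

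**The plan's own figures.** 0.05/5 = 0.01 gives 99% intervals, and 0.05/4 = 0.0125 gives 98.75%. Both match the SAP. The Bonferroni critical values are t(1 - 0.0125/2, 98) = 2.545 and t(1 - 0.01/2, 98) = 2.627.

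**Comparison.** Let c be the value for which P(max |t| <= c) = 0.95 when the visit statistics follow an equicorrelated multivariate t with 98 df, found by numerical integration. Excess width is (Bonferroni value / c) - 1. Familywise error under Bonferroni is P(max |t| > Bonferroni value). Power is for a true difference of 0.5 SD at one visit, with noncentrality 0.5 x sqrt(50/2) = 2.5. Under Bonferroni with four visits it is about 48.5%.

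| Assumed correlation | c, 4 visits | Excess width | Familywise error, Bonferroni | Power using c | c, 5 visits | Excess width | Familywise error, Bonferroni |
|---|---|---|---|---|---|---|---|
| 0.10 | 2.533 | 0.4% | 4.9% | 49% | 2.615 | 0.5% | 4.8% |
| 0.25 | 2.523 | 0.8% | 4.7% | 49% | 2.603 | 0.9% | 4.7% |
| 0.50 | 2.482 | 2.5% | 4.3% | 51% | 2.554 | 2.8% | 4.2% |
| 0.75 | 2.388 | 6.6% | 3.4% | 55% | 2.445 | 7.4% | 3.2% |
| 0.80 | 2.357 | 8.0% | 3.2% | 56% | 2.409 | 9.0% | 2.9% |
| 0.90 | 2.268 | 12.2% | 2.6% | 59% | 2.307 | 13.9% | 2.3% |

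Interval width scales with 1/sqrt(n), so the four-visit gain is equivalent to (2.545/c)^2 - 1 more subjects: about 2% at correlation 0.25, 5% at 0.5 and 17% at 0.8.

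**Correlation that decays with time.** With a spatial-power pattern at the actual visit weeks (simulated, one million draws), the excess width for four and five visits is 1.6% and 2.5% when the correlation at a four-week lag is 0.41, 4.1% and 5.4% at 0.66, and 7.7% and 9.2% at 0.81. The picture is the same.

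**Number of acuity visits.** SAP 1.4.1 and 5.2.1 name four visits for acuity, while the analysis divides by five. That alone widens the acuity intervals by 2.627/2.545 - 1 = 3.2%, whatever the correlation. It is a separate matter, but it decides which columns apply to acuity.

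**The case against.** The strongest reply is that nothing here is wrong. Bonferroni is prespecified, its alphas and interval levels agree, and it holds familywise error at or below 5% under any dependence. It needs no simulation, no seed, no common degrees of freedom and no trust in a covariance structure picked from the data. The hypotheses are exploratory, and the narrower unadjusted intervals will be printed alongside. All of this stands, and it makes the point minor.

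The size is also uncertain. SAP Table 2 uses scenario correlations of 0.25 to 0.75 for slit lamp findings over two eyes and five visits, and Table 3 uses 0.10 to 0.75. Neither is an estimate of between-visit correlation for these endpoints, and SAP section 3 says eyestrain data are being collected for the first time. At 0.25 or below the gain is under 1%. A reader might infer from the upper rows of the table that the intervals are too wide by a known several percent. The documents do not support that.

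A reader might also infer that power is lost for all three endpoints. Acuity and wear time are hypothesised to be statistically no different, with no margin. There, a stricter test makes the hoped-for conclusion easier to reach, so the lost-power argument applies to eyestrain only.

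One part of the reply is weaker than it looks. The planned t-tests already rely on the fitted covariance and its degrees of freedom, so the joint-t method adds little new dependence. If the correlation proves low, its intervals are practically Bonferroni's.

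**Conclusion.** The point holds as an optional gain in efficiency. The planned analysis is valid, and it is conservative to a degree that cannot be fixed from the documents. Under equal correlation and 98 df, Bonferroni intervals exceed joint-t intervals by under 1% at correlation 0.25 or less, 2.5-2.8% at 0.5, 6.6-7.4% at 0.75 and 8-9% at 0.8. Familywise error falls from about 4.9% to about 3% over that range. For eyestrain, power at one visit for a 0.5 SD difference rises by about 1 point at correlation 0.25, 2 to 3 points at 0.5 and 7 points at 0.8. For acuity and wear time the benefit is a tighter interval. Calling the planned intervals erroneous would go too far. What can be said is that the joint-t intervals are never wider, apart from simulation error, and are sharper if the visits are strongly correlated.

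**What to change.** In SAP 5.1.1 and 5.2.2, replace Bonferroni for acuity, wear time and eyestrain by simultaneous p-values and 95% intervals from the joint t distribution of the visit-wise differences, for example by simulation-based adjustment (ADJUST=SIMULATE) with a fixed, stated seed. Keep the unadjusted results.

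Two conditions matter:

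- List the contrasts. The family should be the same-visit Test v Control differences only: four for eyestrain, four for wear time, and for acuity the number settled once the four-visit hypothesis and the five-visit analysis are reconciled. If the adjustment ran over all 28 pairs of the eight lens-by-visit means (8 x 7 / 2), the critical value would be about 3.0-3.1 by simulation at correlation 0.1 to 0.8. That is worse than Bonferroni's 2.545.
- Make the change before anyone sees results by treatment group, including the interim eyestrain analysis in SAP section 3.

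The cost is a sentence or two in the SAP and one program option. SAP 1.1 lets the SAP override protocol section 9 where they differ, so the SAP is the place for it. The small downside is dependence on a seed and on the estimated covariance and degrees of freedom. The latter two are already used by the planned tests.

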5.1.2. Data Handling Rules

Missing or spurious values will not be imputed for the primary or secondary hypotheses. The count of missing values will be included in the summary tables and listings.

Subject dropout is expected to be one of the main reasons of missing data in this clinical trial. Past clinical trials don't provide the evidence that subject dropout is systematic or not-at-random. To evaluate the impact of missing data, sensitivity analysis will be conducted using multiple imputation methods if the proportion of subject dropout is greater than the 15%.

5.2. Efficacy Endpoint(s)

5.2.1. Definition

The primary efficacy endpoints are contact lens monocular distance Visual Acuity (VA) on LogMAR scale using ETDRS charts and Eyestrain caused by glare score. VA will be evaluated under high luminance and high contrast conditions at 4 meters from ETDRS charts. Eyestrain caused by glare will be assessed using eyestrain items and will be scored using Item Response Theory.

The primary efficacy endpoints will be evaluated at 2-, 4-, 8- and 12-week follow-up visits.

The secondary endpoint is daily Average Wearing Time in hours.

The secondary efficacy endpoint will be evaluated at 2-, 4-, 8- and 12-week follow-up evaluations.

5.2.2. Analysis Methods

Efficacy Analysis:

Visual Acuity

Contact lens monocular distance best-corrected visual acuity (BCVA) on LogMAR scale will be analyzed using a linear mixed model to test for the differences between the Test and Control group at each follow-up visit. Lens group, time (1-, 2-, 4-, 8- and 12-weeks) and the interaction between lens and time will be included as fixed effects in the model; and investigator site, subject and eye nested within subject as random effects when appropriate. The covariance between residuals from the same eye and subject at different time points will be selected based on the finite-sample Corrected Akaike's Information Criterion. Covariance structures considered include Compound Symmetry (CS), Heterogeneous Compound Symmetry (CSH), Spatial Power (SP(POW)), *Ante*-dependence (ANTE(1)) and unstructured (UN). For ANTE (1) and SP (POW) structures, site, subject and eye nested within subject will be included as random effects. For the remaining structures only site and subjects will be included as random effects. The covariance structure that returns the lowest Akaike Information Criteria Corrected (AICC) will be selected as the structure that best fit the data. Heterogeneous residuals covariance structures (R-side) across lens groups will be considered when appropriate. The log-likelihood ratio test will be used to test for the homogeneity between the residual covariance structures. The Kenward and Roger method will be used for the denominator degree of freedom.

Comparisons between the Test and the Control groups will be conducted at each time point using a t-test on least-square means from the repeated measure analysis. Adjustment for multiple comparisons across time will be performed using Bonferroni's method with alpha equal to 0.01(0.05/5). The corresponding simultaneous confidence intervals of least-square means differences will be calculated with 99% confidence. Unadjusted multiple comparisons will be calculated with 95% confidence for each comparison.

Average Wear Time (AWT)

AWT (in hours) will be analyzed using a linear mixed model to test for difference between the Test and the Control groups. Lens Group, Time (2-, 4-, 8- and 12-week), and the interaction between lens and time will be included as fixed effects in the model; and site as random effect. The covariance between residuals from the same subject at different time points will be selected based on the finite-sample corrected Akaike's Information Criterion. Covariance structures considered include homogenous compound symmetry (CS), heterogeneous Compound symmetry (CSH), Spatial Power (SP (POW)), Ante-dependence (ANTE (1)) and unstructured (UN). For ANTE (1) and SP (POW) structures, site and subject will be included as random effects. For the remaining structures only site will be included as random effect. The covariance structure that returns the lowest AICC will be selected as the structure that best fit the data. Heterogeneous residuals covariance structures (R-side) across lens groups will be considered when appropriate. The log-likelihood ratio test will be used to test for the homogeneity between the residual covariance structures. The Kenward and Roger method will be used for the denominator degree of freedom.

Comparison between the Test and the Control groups will be conducted at each time point using a t-test on least square means from the repeated measure analysis. Adjustment for multiple comparisons across time (2-, 4-, 8- and 12-weeks) will be performed using Bonferroni's method with alpha equal to 0.0125(0.05/4). The corresponding simultaneous confidence intervals of least-square means differences will be calculated with 98.75% confidence. Unadjusted multiple comparisons will be calculated with 95% confidence for each comparison.

Eyestrain caused by glare score

Eyestrain items will be scored using item response theory. A lower score indicates less eyestrain, whereas higher score indicates more eyestrain. Eyestrain score will be analyzed using a linear mixed model to test for difference between the Test and the Control groups. Lens Group, time (2-, 4-, 8- and 12-week), iris category and all interactions between lens group, time and iris category will be included as fixed effects in the model; and site as random effect. The covariance between residuals from the same subject at different time points will be selected based on the finite-sample corrected Akaike's Information Criterion. Covariance structures considered include homogenous compound symmetry (CS), heterogeneous Compound symmetry (CSH), Spatial Power (SP (POW)), Ante-dependence (ANTE (1)) and unstructured (UN). For ANTE (1) and SP (POW) structures, site and subject will be included as random effects. For the remaining structures only site will be included as random effect. The covariance structure that returns the lowest AICC will be selected as the structure that best fit the data. Heterogeneous residuals covariance structures (R-side) across lens groups will be considered when appropriate. The log-likelihood ratio test will be used to test for the homogeneity between the residual covariance structures. The Kenward and Roger method will be used for the denominator degree of freedom.

If the interaction between lens and iris category is significant at the 15% significance level, then comparison between lenses within each iris category will be conducted. If the interaction between lens, iris category and time is significant at the 15% significance level, then comparison between lenses within each iris category at each timepoint will be conducted.

Comparison between the Test and the Control groups will be conducted at each time point using a t-test on least-square means from the repeated measure analysis. Adjustment for multiple comparisons across time will be performed using Bonferroni's method with alpha equal to 0.0125 (0.05/4). The corresponding simultaneous confidence intervals of least-square means differences will be calculated with 98.75% confidence. Unadjusted multiple comparisons will be calculated with 95% confidence for each comparison.

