Contact lens monocular distance best-corrected visual acuity (BCVA) on logMAR scale will be analyzed using a linear mixed model to test for the differences between the Test and Control group at each follow-up visit. Lens group, time (1-, 2-, 4-, 8- and 12-week) and the lens group by time interaction will be included as fixed effects in the model; and investigator site, subject and eye nested within subject as random effects when appropriate.

The covariance between residuals from the same eye and subject at different time points will be selected based on the finite-sample Corrected Akaike's Information Criterion. Covariance structures considered include Compound Symmetry (CS), Heterogeneous Compound Symmetry (CSH), Spatial Power (SP(POW)), *Ante*-dependence (ANTE(1)) and unstructured (UN). For ANTE(1) and SP(POW) structures, site, subject and eye nested within subject will be included as random effects. For the remaining structures only site and subjects will be included as random effects. The covariance structure that returns the lowest Akaike Information Criteria Corrected (AICC) will be selected as the structure that best fit the data. Heterogeneous residuals covariance structures (R-side) across lens groups will be considered when appropriate. The log-likelihood ratio test will be used to test for the homogeneity between the residual covariance structures. The Kenward and Roger method will be used for the denominator degree of freedom.

Comparison between the Test and the Control groups will be conducted at each time point using a t-test on least-square means from the repeated measure analysis. Adjustment for multiple comparisons across time will be performed using Bonferroni's method with alpha equal to 0.01 (0.05/5). The corresponding simultaneous confidence intervals of least-square means differences will be calculated with 99% confidence.

Average Wear Time (AWT)

AWT (in hours) will be analyzed using a linear mixed model to test for difference between the Test and the Control groups. Lens Group, Time (1-, 2-, 4-, 8- and 12-week) and the interaction term the lens group by time will be included as fixed effects in the model; and site as random effect.

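### The logMAR model has no term for covariance between a subject's two eyes at the same visit, so per-visit standard errors are modestly too small if the eyes share a visit-specific deviation

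*SAP*

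**What the plan says.** SAP 5.2.2 (Visual Acuity) and Protocol 9.1 describe the same linear mixed model for monocular logMAR, with lens group, time and their interaction as fixed effects. The general list of random effects is "investigator site, subject and eye nested within subject as random effects when appropriate".

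The residual part is described so: "The covariance between residuals from the same eye and subject at different time points will be selected" by corrected AIC from CS, CSH, SP(POW), ANTE(1) and UN. For ANTE(1) and SP(POW), "site, subject and eye nested within subject will be included as random effects". For CS, CSH and UN: "For the remaining structures only site and subjects will be included as random effects".

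Test and Control are compared by tests "conducted at each time point using a t-test on least-square means from the repeated measure analysis". On inference, "The Kenward and Roger method will be used for the denominator degree of freedom"; no empirical (sandwich) variance is named. SAP 5.1.1 sets a "two-sided type I error rate of 5% for primary and secondary hypotheses". For acuity, SAP 5.2.2 uses 0.01 (0.05/5) per visit with 99% intervals, and also reports unadjusted 95% intervals.

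**The concern.** Each candidate structure says how one eye's residuals relate from visit to visit. Across the two eyes, the only shared terms are site and subject, and these take the same value at every visit. The model therefore forces the between-eye covariance within one visit to equal that between different visits.

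In Protocol 4.7.1, Visits 3 to 6, the right and left eyes are read one after the other in a single ETDRS step. Attention, fatigue, lens age and the lighting on that day could move both readings together. The model would treat such a shared shift as two independent eye residuals and so credit the pair with more information than it carries. Corrected AIC cannot detect this, because no candidate contains the term. Allowing different residual covariances by lens group does not add it either, and Kenward-Roger works from the fitted model. At stake is the validity of the per-visit tests and intervals for a co-primary endpoint.

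**Working it through.** **The plan's own acuity figures.** SAP Table 3 is the only acuity calculation. It uses one common correlation and gives no variance components, so the quantity needed here cannot be taken from it. Its cells are reproduced, to within 0.11 percentage points, only as one minus power, with n = 2 and one-sided alpha 0.01. For effect size 0.50 and rho 0.10: sqrt(0.5 × 50 × 2 × 0.25 / 1.10) − 2.326 = 1.045, giving power 85.2%, where the table prints 14.8%. That is a separate matter and nothing below depends on it.

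**Inputs from the documents.** 50 completers per arm; two eyes; T = 4 logMAR visits (2, 4, 8 and 12 weeks, SAP 5.2.1); two-sided 0.05 and 0.01.

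**Assumed inputs.** Scale per-eye variance to 1. Let s be the subject share and v the subject-by-visit share; the rest is eye and residual. The documents give neither s nor v.

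**Formula (balanced data).**
- True variance of a subject's two-eye mean at one visit: (1 + s + v)/2.
- The model has one constant for the between-eye covariance. It settles at the average over all pairs of visits, s + v/T, while total variance is estimated correctly. Model variance: (1 + s + v/T)/2.
- Shortfall: v(T − 1)/(2T), which is 0.375v at T = 4.
- SE ratio (model/true) = sqrt[(1 + s + v/4)/(1 + s + v)].
- True two-sided error = 2Φ(−z × ratio), with z = 1.960 or 2.576.

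| s | v | SE ratio | Error at nominal 0.05 | Error at nominal 0.01 |
|---|---|---|---|---|
| 0.4 | 0 | 1.000 | 5.0% | 1.0% |
| 0.4 | 0.05 | sqrt(1.4125/1.45) = 0.987 | 5.3% | 1.1% |
| 0.4 | 0.10 | sqrt(1.425/1.50) = 0.975 | 5.6% | 1.2% |
| 0.4 | 0.20 | sqrt(1.45/1.60) = 0.952 | 6.2% | 1.4% |
| 0.3 | 0.30 | sqrt(1.375/1.60) = 0.927 | 6.9% | 1.7% |

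The last row changes both shares. With s held at 0.4, v = 0.30 gives 0.931, with error 6.8% and 1.6%.

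**Checks.** Fitting each of the five structures to the true covariance gave the same ratio for all five at v = 0, 0.10, 0.20 and 0.30. Simulation of the CS model (8,000 trials per setting, 50 per arm) gave SE ratios of 0.980, 0.950 and 0.927 at v = 0.10, 0.20 and 0.30. Error was 5.3, 6.1 and 6.8% at nominal 0.05, and 1.1, 1.3 and 1.6% at nominal 0.01. With a subject-by-visit term added, it was 4.7 to 4.9% and about 0.9%.

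**Family-wise error at 0.01 per visit.** Four visits, normal approximation, eye share assumed 0.1:

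| s | v | Family-wise error |
|---|---|---|
| 0.4 | 0.05 | 3.5% |
| 0.4 | 0.10 | 3.9% |
| 0.4 | 0.20 | 4.6% |
| 0.2 | 0.10 | 4.5% |
| 0.2 | 0.20 | 5.5% |
| 0.3 | 0.30 | 6.0% |

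**The case against.** *The residual block might be the whole subject.* UN could then pick up same-visit covariance between eyes. The neighbouring text rules this out. For wear time and eyestrain, with one value per subject per visit, the subject effect is dropped under CS, CSH and UN because the residual block already is the subject. For acuity under the same structures, the subject effect is kept and the eye effect is dropped. That makes sense only if the block is the eye.

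*The shared deviation is an assumption.* This stands. The protocol bounds the lighting (room above 7.3 EV, chart 9.9 to 10.7 EV) and uses different charts for the two eyes. That limits the lighting route without closing it, since 0.8 EV is about a 1.7-fold luminance range (2^0.8). Attention and fatigue remain plausible but unmeasured. If v is zero, there is no error.

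*The multiplicity rule absorbs much of the effect.* This stands for the adjusted analysis. A reader might infer that overall error control for acuity is lost. The documents do not support that: 0.01 is used per visit although the endpoint is assessed at four visits, and family-wise error passes 5% only at the larger assumed shares. The cushion depends on there being four tests. The model text lists five times and the schedule table ticks logMAR for all follow-ups as a group, but the detailed Visit 2 steps contain no ETDRS reading. The unadjusted 95% intervals have no such cushion.

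*The direction works against the sponsor's claim.* This stands. A reader might infer that the model makes it easier to conclude that the lenses do not differ. The hypothesis is no statistical difference, so standard errors that are too small produce more rejections, not fewer. No equivalence margin is set against which a narrow interval would be judged.

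**Conclusion.** The structural point holds: no candidate acuity model in SAP 5.2.2 or Protocol 9.1 allows the two eyes to covary more within a visit than across visits. For any positive subject-by-visit variance, the model-based standard errors of the per-visit comparisons are too small under all five structures.

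The size is conditional. It rests on assumed variance shares, near-balanced data (plausible, since the efficacy set is completers) and four visits. Over the range shown, the understatement is about 1 to 7%. With five visits it is slightly larger: ratios of 0.973 and 0.949 at v = 0.10 and 0.20, with s = 0.4.

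The consequence is too many false acuity differences, and 95% and 99% intervals that claim too much precision. Both documents call the hypotheses exploratory, so this is a modest correction and not a threat to the study's conclusions.

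**What to change.** In SAP 5.2.2 (Visual Acuity), add a random subject-by-visit effect to each of the five candidate models, so that same-visit covariance between eyes is estimated. State in advance that, if this does not converge, the two-eye mean logMAR per visit will be analysed in a repeated-measures model of the form already planned for wear time. SAP 1.1 lets the SAP override Protocol section 9, so the change can be made there.

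The cost is one more variance parameter per candidate, some added risk of non-convergence in models that already carry site and subject effects, and slightly wider intervals. If the shared variance is negligible, its estimate will be near zero and the results will hardly change.
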